#### **11.1.4 Colon Preparation**

Subjects will be instructed to follow a detailed dietary and colon preparation regimen prior to the procedure day. All colon preparation products will be standard colon cleansing products approved by the FDA.

Patients will be randomized to one of two bowel preparation regimens (instruction for bowel preparation for morning and afternoon procedures are provided in appendix B1 and B2).

Subjects will keep a timed diary of key preparation steps and bowel activity, in addition questions about the patients satisfaction from the bowel preparation regime and diet instruction will be captured (Appendix D).

#### **11.1.5 Colonoscopy procedure (Visit 2)**

##### Pre-Examination Procedures

- Verify eligibility checked and informed consent was obtained after explaining all risks, benefits, and alternatives to the candidate.
- Verify that the research assistant has collected completed diaries from the subject.
- Verify all background/clinical information, demographic and medical history was documented

Note: Subjects that did not take the bowel preparation or failed to complete the bowel preparation will not undergo the procedure and will be excluded from the study.

- Verify all connections and assembles are properly attached (see Instructions for Use)
- Verify device works properly (see Instructions for Use)
- Place and prepare the subject for the procedure as per standard colonoscopy.
- Perform a digital rectal exam as per standard colonoscopy, evaluate the adequate level of the preparation and start the colonoscopy procedure with the Pure-Vu System as per standard of care.

##### Pre-Examination Procedures

The procedure will be performed by the clinical investigator(s), experienced in GI endoscopy according to local standard of care. Anesthesia will be applied as well per the standard of care. In CL00042/ Protocol, Version 1.0 December 13, 17

Document title:	Document No.	Version	Page 28 of 61
Optimizing the Preparation Regime Prior to Colonoscopy Procedure with Pure-Vu System	CL00042	1.0	

order to ensure correct operation of the Pure-Vu System a Motus GI representative may attend the procedure. Using the Pure-Vu, requires specific training with the device that will be provided by the sponsor prior to the study. Pure-Vu System operation is described in the Instruction for Use.

### Colonoscopy Procedures

The colon preparation level for each colorectal segment (ascending, transverse and descending) before the cleansing operation during the insertion phase and post the cleansing operation during withdrawal will be evaluated using the BBPS scoring index (Appendix C).

Once the procedure is completed, relevant data will be recorded on the CRF in addition, findings, diagnosis as well as Physician questionnaire will be recorded/completed.

The colonoscopy examination with the Pure-Vu will be recorded on VCR or DVD. Only the subject study ID and initials should appear in the recorded video.

The cecum will be documented in a picture.

All optical colonoscopy still pictures will be saved in a digital format. Quality copies of the pictures taken during optical colonoscopy will be provided to the sponsor with the optical colonoscopy report.

These videos and pictures will be archived and may be used in future analyses to, for example, provide further information about observed lesions or to assess study quality.

### **Specific situations occurring during colonoscopy**

- If the attempt to reach the cecum is failed, the investigator shall perform the procedure with a pediatric or any other colonoscope he/she may choose without the Pure-Vu. The subject will complete the study as planned.
- If a medical condition requiring treatment is detected during colonoscopy, the subject will be treated as per the standard care.

### Post-Examination Follow-up

Subjects will be transferred to recovery room for observation per standard colonoscopy protocol. Subjects will be contacted by phone 2 working days after the procedure to verify that there has been no change in their well-being. Any AE will be documented in the CRF.

In addition questions about the patients' satisfaction with the Pure-Vu procedure will be completed.

Document title:	Document No.	Version	Page 29 of 61
Optimizing the Preparation Regime Prior to Colonoscopy Procedure with Pure-Vu System	CL00042	1.0	

Before a subject is considered “lost to follow-up”, there must be at least two documented attempts to contact the subject.

## **11.2 Required Concomitant Medications or Therapies**

All the medications used in this study are FDA approved, Commercial off-the-shelf products.

## **12.0 Statistical Analysis**

### **12.1 Sample Size Determination**

This is a pilot study that will include up to 100 patients; no statistical considerations were made to determine the sample size.

### **12.2 Description of statistical methods**

Basic demographic and other baseline characteristics will be collected and analyzed for all patients. Summary statistics (arithmetic mean, standard deviation, median, minimum and maximum for quantitative variables) will be presented for the total study population. Frequency tables for qualitative data will be provided.

Any deviation from specified statistical plan will be in addition to “per protocol” analysis and will be reported as such. Intent-To-Treat and Post-hoc analysis will be conducted according to the existing data gathered, if necessary.

In addition, in cases of an incomplete procedure (i.e., the entire colon is not visualized); the overall BBPS per patient will be evaluated based on the colon segments that were visualized.

### **12.3 Primary Endpoint Hypothesis Analysis**

The primary endpoint is the rate of adequate bowel cleansing level after the use of the Pure- Vu.

The rate of adequate cleansing level in each colon segment before and after use of Pure-Vu will be evaluated using the Boston Bowel Preparation Scale (BBPS).

A score of 0 - 3 will be given to each of the 3 segments of the colon (Descending, Transverse and Ascending).

Document title:	Document No.	Version	Page 30 of 61
Optimizing the Preparation Regime Prior to Colonoscopy Procedure with Pure-Vu System	CL00042	1.0	

BBPS scores will be rated by the endoscopist, on the basis of three segment scores summed for maximum score of 9, where:

- 0 = unprepared
- 9 = completely clean (in completed to Cecum procedures)

*An adequate cleansing procedure is defined as when all 3 colon segments are graded as 2 or 3.*

Chi-square or Fisher's exact test, as appropriate, will be performed in order to compare proportions of good or excellent cleansing level between the two preparation procedures.

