### 3.0 Protocol Synopsis

Study Summary					
Study Purpose	To determine the optimal bowel preparation regimen for Pure-Vu System procedures in patients indicate for colonoscopy procedure.				
Objective	The primary objective of this multicenter, prospective, randomized study is to evaluate the performance of Pure-Vu System in cleansing patients' colon who are indicated for a colonoscopy procedure using one of two different reduce bowel preparation regimes.in addition, the cecum intubation rate, time to cecum, total procedure time, and adverse event will be evaluated.				
Test and Comparator Procedures	Prep A	Prep B			
5 days prior procedure day					
No seedy food					
1 day prior procedure day					
Low residue diet;					
Spilt dose of 15 oz Magnesium Citrate + 39 oz of clear liquid		Spilt dose of 10 oz Magnesium Citrate + 32oz of clear liquid			
Procedure Day					
Clear-liquid diet up to 3 hours prior to the procedure					
Fasting (no food / liquids) start 3 hours prior to procedure time					
*At least 2 liter water per day during the preparation days.					

Document title:  Optimizing the Preparation Regime Prior to Colonoscopy Procedure with Pure-Vu System	Document No.  CL00042	Version  1.0	Page 8 of 61
---	------------------------------------	---------------------------	-----------------

Protocol Number	CL00042
Protocol Title	Optimizing the Preparation Regime Prior to Colonoscopy Procedure with Pure-Vu System Rev 1.0
Study Sponsor	Motus GI Medical Technologies, [name] [contact] [contact]
Sponsor Representative	[name] Director of Clinical Affairs
Study Type	Multicenter, prospective, randomized feasibility study
Study Product	Pure-Vu System
Study Phase	Post-market
IDE Number	K173392 Class II
Study Location	United States
Study Duration	Study period will last approx. 12 months
Study Design	Patients will be randomized to receive one of two bowel preparation regimens prior to colonoscopy with Pure-Vu procedure.
Planned Follow-Up	Telephone follow-up will be conducted at 2-3 working days post-procedure to assess subject well-being and capture any adverse events.
Subject Population	Subjects indicate for colonoscopy procedure

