Document title:  Optimizing the Preparation Regime Prior to Colonoscopy Procedure with Pure-Vu System	Document No.  CL00042	Version  1.0	Page 9 of 61
---	------------------------------------	---------------------------	-----------------

Planned # of Subjects	Up to 100 subjects
Planned # of Sites	Up to 3 clinical sites
Primary Endpoint	The rate of adequate cleansing level per patient will be evaluated by the BBPS(1) scoring index post the cleansing operation in both study arms.
Secondary Outcomes	The following secondary outcomes will be determined : 
 
• Adverse events
 
• Cecal intubation rate
 
• Time to Cecum
 
• Total procedure time
 

Randomization	Block randomization will be employed for each site to assign subjects to one of the two bowel preparation arms (Prep A versus Prep B).
Eligibility Criteria	
Inclusion Criteria
 
 
1. Subjects scheduled for colonoscopy procedure
 
2. Subjects in the age range 22-75 years inclusive
 
3. Subject is willing and able to participate in the study procedures and to understand and sign the informed consent.
 
 
Exclusion Criteria
 
 
1. Patients with active Inflammatory Bowel Disease
 
2. Patients with known diverticulitis disease or with prior incomplete colonoscopy due to diverticular disease
 
3. Patients with known bowel obstruction
 
4. Patient with chronic constipation
 
5. History of prior surgery to colon and/or rectum
 

Document title:  Optimizing the Preparation Regime Prior to Colonoscopy Procedure with Pure-Vu System	Document No.  CL00042	Version  1.0	Page 10 of 61
---	------------------------------------	---------------------------	------------------

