## Statistics

Primary Endpoint Analysis	
The primary endpoint is the rate of adequate bowel cleansing level, as determined by Boston Bowel Preparation Scale (BBPS), assessed per patient in both study arms.
 
Chi-square or Fisher's exact test, as appropriate, will be performed in order to compare the proportions of good or excellent cleansing level (i.e., BBPS>1 in all colon segments) post cleansing procedure between the two study arms.

Secondary Analyses	
Cecum intubation rate
 
Proportion tests (Chi-square or Fisher's exact) will be performed in order to compare between the two preparation procedures cecum intubation rate
 
Time analysis
 
T-tests for continuous variables will be performed in order to evaluated the difference between Prep A and Prep B for the following:
 

• Total procedure time

Document title:  Optimizing the Preparation Regime Prior to Colonoscopy Procedure with Pure-Vu System	Document No.  CL00042	Version  1.0	Page 11 of 61
---	------------------------------------	---------------------------	------------------

	

• Time to cecum

 
Safety analysis
 
Individual listings of adverse events including type of device, adverse events (reported term) start date, duration, and severity will be provided.

Determination of Sample Size	This is a pilot study that will include up to 100 patients; no statistical considerations were made to determine the sample size.
Interim analyses	No Interim analysis is planned.

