The current study is designed to evaluate the efficacy of two different reduced preparation regimen intended for use with Pure-Vu System. The study objectives are to compare cleansing levels, cecum intubation rate, the time to cecum, the total procedure time, and adverse event (AE) rates following use of the two different bowel preparation methods in subjects undergoing standard colonoscopy.

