## 8.0 Study Objectives

### 8.1 Primary objective

To evaluate the performance of Pure-Vu System in cleansing patients' colon who are indicated for a colonoscopy procedure using one of two different bowel preparation regimes.

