### Study Flow chart

#### 9.1 Primary Endpoint

The primary endpoint is the rate of adequate cleansing level per subject evaluated by the BBPS scoring index pre- and post the cleansing operation.

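### Section 9.1 gives the primary endpoint a different time point from the synopsis and section 12.3, and two secondary analyses use valid but inefficient tests

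*Protocol*

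**What the plan says.** **Time point of the primary endpoint.**
- Synopsis, Primary Endpoint: BBPS adequacy is scored "post the cleansing operation in both study arms".
- Synopsis, Primary Endpoint Analysis: the proportions are compared "post cleansing procedure between the two study arms".
- Section 9.1: the rate is "evaluated by the BBPS scoring index pre- and post the cleansing operation".
- Section 12.3, opening: the endpoint is the "rate of adequate bowel cleansing level after the use of the" device. The next sentence says that segment rates before and after the device will be evaluated. The test sentence then says that chi-square or Fisher's exact test "will be performed in order to compare proportions of good or excellent cleansing level between the two preparation procedures", with no time point.
- Section 5.1 is general: "The study objectives are to compare cleansing levels, cecum intubation rate, the time to cecum, the total procedure time" and adverse event rates.

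**Site.** Section 11.1.2 randomises in blocks within each site. Section 12.4 (Time analysis) compares time to cecum and total procedure time by t-test, with no site term.

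**Questionnaires.** Section 12.4 assigns chi-square or Fisher's exact test, as appropriate, to patient and user satisfaction without separating item types. Appendix E has five-level items from very easy to very difficult, and Appendix F has five-level usability items from excellent to unacceptable. Other items are yes/no.

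**The concern.** Section 9.1 is where a reader looks for the definition of the primary endpoint. As worded, it could mean the post-cleansing rate, both rates, or a change. These are different estimands, and only the first matches the synopsis. The 12.3 test sentence does not settle the matter alone, because it carries no time point and follows a sentence on before-and-after rates.

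The other two points are about efficiency. Blocking by site removes site differences from the arm contrast, but a t-test that ignores site leaves them in the error term. A chi-square test on five ordered levels treats them as unordered labels. Section 12.7 says that the pilot should show which regimen tends to do better, so precision that the data already hold is worth keeping.

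**Working it through.** The protocol has no sample-size or power figure to reproduce; section 12.1 says that none was made. Two-sided 5% tests are assumed throughout.

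**1. Time point.** Side by side:

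| Place | Time point |
|---|---|
| Synopsis, Primary Endpoint | post |
| Synopsis, Primary Endpoint Analysis (the test) | post |
| Section 9.1 | pre and post |
| Section 12.3, definition | post |
| Section 12.3, test sentence | none given |

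The dated statements other than 9.1 agree.

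**2. Site term.** Input: 15 patients per arm at each site (section 9.0), with 3 sites (synopsis), so 45 per arm. Section 9.0 also allows up to 10 sites, which is treated below as a sensitivity case. The between-site share of variance is not in the protocol and is assumed.

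Let σw² and σb² be the within-site and between-site variances, summing to 1. With equal arms in each site, site effects cancel in the arm difference, whose variance is 2σw²/45. In each arm, the sum of squares picks up an expected 15 × 2 × σb² = 30σb² from sites, so 60σb² over both arms, on 88 degrees of freedom. The t-test therefore uses, on average,

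σw² + (60/88)σb² = σw² + 0.682σb².

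At a 20% site share this is 0.8 + 0.682 × 0.2 = 0.936 where 0.8 is right. √(0.936/0.8) = 1.08, so the confidence interval is about 8% too wide. Simulation (20,000 runs, true difference 0.6 total SD) agrees:

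| Site share | Size, plain / with site | Power, plain / with site | Points lost | CI too wide by |
|---|---|---|---|---|
| 0% | 5.1% / 5.1% | 80.1% / 80.1% | 0 | 0% |
| 5% | 4.9% / 5.2% | 81.1% / 82.1% | 1.0 | 2% |
| 10% | 4.4% / 5.1% | 82.5% / 84.4% | 1.9 | 4% |
| 20% | 3.6% / 4.8% | 84.9% / 88.2% | 3.3 | 8% |
| 30% | 3.1% / 5.1% | 86.9% / 92.2% | 5.3 | 13% |

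With 10 sites of 5 per arm and a 20% share, size is 2.9% against 5.0%, and power 87.5% against 91.5%.

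**3. Ordered items.** Input: a five-level item, 45 per arm. Each cumulative odds in one arm is multiplied by a common odds ratio. For equal fifths and an odds ratio of 2, the first level goes from odds 0.2/0.8 = 0.25 to 0.50, that is from 20% to 33%. Chi-square spreads this one-directional shift over 4 degrees of freedom; a rank test puts it on one. Three assumed baseline distributions were used: equal fifths; 10/20/40/20/10%; and 30/35/20/10/5%. Simulated power (4,000 runs each):

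| Odds ratio | Chi-square | Rank test |
|---|---|---|
| 1 (size) | 4.2–5.6% | 4.8–5.3% |
| 1.5 | 10–11% | 18–19% |
| 2.0 | 25–26% | 44–46% |
| 2.5 | 40–45% | 64–67% |
| 3.0 | 56–61% | 79–82% |

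**4. Pre-cleansing BBPS by arm, for the optional suggestion only.** The earlier study in section 6.3, with a different preparation, had 25% adequate before Pure-Vu. Under the plan's own rule (Fisher if an expected count is below 5, else chi-square), 25% against 44% has about 49–52% power at 45–50 per arm. A shift in the 0–9 total that a t-test would detect with 80% power (0.597 or 0.566 SD) corresponds to about 25% against 46–47% adequate, by normal approximation. As a yes/no comparison that has about 59% power.

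**The case against.** **On the time point.** The plan can already be read correctly. The synopsis dates the test, and 12.3 opens with a post-cleansing definition, so its undated sentence is naturally read the same way. That stands: this is one inconsistent definition. A reader might infer that the synopsis, 9.1 and 12.3 each say something different. They do not; only 9.1 departs.

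**On the tests.** Both are valid, and site adjustment is commonly left to an analysis plan, which is not at hand. No other arm comparison in section 12 has a site term either. The losses rest on assumed site variance and answer distributions. Usability ratings come repeatedly from the same physicians, whereas the simulation takes them as independent. The questionnaire section also says "as appropriate" in substance, but only as a choice between chi-square and Fisher. All of this limits the size of these points. It does not remove them: the protocol names specific tests, and better-matched ones cost almost nothing.

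**On the missing pre-cleansing comparison.** A reader might infer that the post-cleansing primary is the wrong endpoint, because the purpose is "To determine the optimal bowel preparation regimen for Pure-Vu System procedures" and pre-cleansing BBPS is the direct readout of each preparation. The documents do not support that. The primary objective is to "evaluate the performance of Pure-Vu System in cleansing" the colon under either regimen, so the result after the device is the relevant one. The pre-cleansing scores are collected (section 11.1.5, Appendix F), and not listing an arm contrast of them is no contradiction. Such a contrast would also rest on unblinded endoscopist scoring. A 0–9 total is not comparable when a segment was not seen, since sections 12.2 and 12.5 score only the visualised segments.

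**Conclusion.** The point holds as three inexpensive corrections. First, section 9.1 conflicts with the synopsis and with the definition in 12.3 and must be reconciled; this is the only contradiction, and it needs no assumption. Second, the t-test for procedure times ignores the randomisation stratum. It is conservative, not biased: no loss if sites do not differ, and about 3 to 4 points of power with size about 3.6% at an assumed 20% site share. Third, chi-square or Fisher on five-level ordered items gives up power: about 25% against about 45% at an odds ratio of 2, under the assumed distributions.

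No stated test is invalid. Sample size is not at issue either, because sections 12.1 and 12.7 declare an unpowered pilot. The absence of a pre-cleansing arm comparison is at most a low-priority suggestion.

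**What to change.** 1. In section 9.1, and in the test sentence of section 12.3, state that the primary endpoint is adequacy after the cleansing operation, as the synopsis does.
2. In section 12.4, compare time to cecum and total procedure time with a linear model containing arm and site.
3. In section 12.4, use a rank test (Wilcoxon) for the ordered satisfaction and usability items, and keep chi-square or Fisher's exact test for yes/no items.

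Optional, low priority: report pre-cleansing BBPS by arm as an exploratory description, restricted to patients with all three segments scored and labelled as unblinded endoscopist scoring. A blinded re-read of the recordings would need extra readers and is not requested.

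Cost: wording in sections 9.1, 12.3 and 12.4. There are no new patients, visits or CRF fields.

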## 12.4 Effectiveness Analyses

### Safety Analysis

The secondary endpoint is to evaluate the Device related adverse event and the overall adverse events rate. The safety analysis set will consist of all patients who were enrolled into the study.

Individual listings of adverse events including type of device, adverse events (reported term), seriousness, duration, relationship to the study device, severity and the adverse events outcome will be provided for the total population and per study arm. AEs will be summarized using frequency counts and percentages per study arm.

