## 7.0 Risk/Benefit Analysis

### 7.1 Anticipated Risks Associated with Pure-Vu System conjunction with a standard colonoscope

The Pure-Vu is used in conjunction with a standard colonoscope during a colonoscopy procedure. Hence, the complications associated with using the Pure-Vu are anticipated to be similar to those associated with the colonoscopy procedure. As with any colonoscopy procedure, when using the Pure-Vu there is some risk of bowel perforation, pain, infection and bleeding. Although the risks of the procedure with the Pure-Vu System are expected to be comparable to conventional colonoscope (0.35%), the device is an Oversleeve to a standard colonoscope. Hence, diameter is bigger, and the cleansing time may add some minutes to the procedure time. a potential risks associated with the participation in the clinical investigation may include a repeated colonoscopy procedure as the subjects enrolled to the study are required to undergo a limited prep as compared to the preparation given prior to standard colonoscopy procedure.

The latest Pure-Vu version was tested in an animal study including 35 pigs and in preliminary clinical studies including 97 subjects.

Document title:	Document No.	Version	Page 19 of 61
Optimizing the Preparation Regime Prior to Colonoscopy Procedure with Pure-Vu System	CL00042	1.0	

No major complication or serious adverse events occurred within the course of those studies.

In addition, these clinical studies demonstrated an excellent cleansing effectiveness; Pure-Vu improved the cleansing level from 25% at baseline to 99% after the cleansing was operated and in 98% of the patients the cecum was reached and the procedures completed successfully. Efficacy results support the study design rationale that decreases the risks associated with the preparation without increasing the risk related to incomplete/ repeated colonoscopy procedure.

Lastly, patients to be enrolled to this study shall be eligible to colonoscopy, thus the risks detailed above covers all the population intended to participate in the study.

Considering the residual risks and the potential and the risk against benefit assessment, it can be concluded that the system may offer potential benefit to the patients along with no significant risk increase.

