## 7.2 Anticipated Risks Associated with bowel preparation agents

The Bowel preparation agent used in this study are approved in U.S.

The main anticipated risks associated with the bowel preparation agents including nausea with or without vomiting, abdominal pain and dehydration.

The preparation in this study is less intensive compared to the standard preparation done prior to colonoscopy procedure, thus we expect that the risks related to the preparation agent will be similar or even lower than the risks following a standard preparation to colonoscopy procedure.

Reduction of the bowel preparation regimen will minimize patient discomfort and AEs associated with bowel cleansing, and potentially maximize the efficacy of the colonoscopy procedure with Pure-Vu System.

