### **13.3 Adverse Device Effect (ADE)**

An Adverse Device Effect (ADE) is an AE related to the use of an investigational medical device.

This definition includes AEs resulting from insufficient or inadequate instructions for use, deployment, implantation, installation, or operation, or any malfunction of the investigational medical device.

This definition includes any event resulting from use error or from intentional misuse of the investigational medical device.

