### 13.7 Adverse Event Relationship Classification

Relationship to study product administration will be determined as follows:

- *No Relationship*: No relationship between the AE and the administration of study treatment and a known relationship to other etiologies such as concomitant medications, procedure, or subject's clinical state.
- *Possible Relationship*: An AE that follows a reasonable temporal sequence from administration of the study treatment and follows a known response pattern to the study treatment but could have been produced by the participant's clinical state or by other therapies.
- *Probable Relationship*: An AE that follows a reasonable temporal sequence from administration of the study treatment; follows a known response pattern to the study treatment; and cannot be reasonably explained by the known characteristics of the participant's clinical state or by other therapies.
- *Definite Relationship*: An AE that follows a plausible temporal sequence from administration of the study treatment and follows a known response pattern to the study treatment. The reaction cannot be reasonably explained by the known characteristics of the subject's clinical state or other modes of therapy administered to the subject.

Document title:	Document No.	Version	Page 35 of 61
Optimizing the Preparation Regime Prior to Colonoscopy Procedure with Pure-Vu System	CL00042	1.0	

- *Unknown/Impossible to Determine:* Given the information available, sequence and timing of events, it is unknown or impossible to determine the relationship of the AE with the study treatment.

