**Report Serious Adverse Event (SAE) within 48 hours of learning the event**

Adverse Event (AE) Form	Please Check
Have any AEs occurred during the study?	Yes / No
If yes,	
Start Date	__ / __ / __ DD MM YY
End Date	__ / __ / __ DD MM YY
Description:	
 
• Tissue trauma
 
• Excessive bleeding
 
• Laceration
 
• Other: _____
 
• Death
 

Severity	
 
• Mild
 
• Moderate
 
• Severe
 

Anticipated	Yes / No
Relation to the study	
 
• Unrelated
 
• Unlikely
 
• Possibly
 
• Related
 

Was the AE serious AE?	Yes / No
If yes, specify the reason	
 
• Death
 
• Life threatening
 
• Hospitalization
 
• Persistence / significant disability / incapacity
 
• Congenital anomaly / birth defect
 
• Important medical event (subject's health is at risk and intervention is required to prevent one of the above events) , specify
 

Document title:  Optimizing the Preparation Regime Prior to Colonoscopy Procedure with Pure-Vu System	Document No.  CL00042	Version  1.0	Page 61 of 61
---	-----------------------------	--------------------	------------------

	Date of Event report to the IRB:  ____ / ____ / ____ DD MM YY
Treatment?	Yes / No
If yes, specify type and reason	Pharmacological treatment  _____
	Other medical intervention  _____
Outcomes	

• Resolve

• Improved

• Unchanged

• Worsen

• Insufficient follow up

• Comments: _____

Investigator signature	_____
Date	____ / ____ / ____ DD MM YY

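### The AE form does not ask about relationship to Pure-Vu, so for events that device or preparation could cause it does not give the device-related AE rate of 12.4; the safety set is also stated two ways

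*Protocol*

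**What the plan says.** Safety is a secondary objective in section 8.2, framed as safety of Pure-Vu in each arm. Section 12.4 turns this into an endpoint: "The secondary endpoint is to evaluate the Device related adverse event and the overall adverse events rate". It asks for listings that include each event's relationship to the study device, and for counts and percentages by arm.

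Section 13.7 introduces a five-grade causality scale with "Relationship to study product administration will be determined as follows". Its grade definitions then speak of study treatment. Section 13.3 defines the device event: "An Adverse Device Effect (ADE) is an AE related to the use of an investigational medical device".

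The AE form in Appendix F has a single causality item, labelled "Relation to the study", with the options Unrelated, Unlikely, Possibly and Related.

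On the population, section 12.4 says "The safety analysis set will consist of all patients who were enrolled into the study", and section 11.1.3 counts a patient as enrolled once the consent form is signed. Section 12.5 instead puts into the safety analysis everyone who undergoes bowel preparation. Section 11.1.5 says that patients who do not take or do not finish the preparation will not have the procedure and leave the study. Section 13.1 collects AEs from enrolment to the end of follow-up.

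**The concern.** Every patient who reaches the procedure has had two study exposures, a purgative and the device. Both belong to the study, so a tick against Related does not say which exposure the investigator had in mind. The endpoint needs exactly that distinction. An analysis plan can define how grades are grouped, but it cannot supply a judgement that the form does not ask for.

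The denominator matters too. The two descriptions of the safety set differ by screen failures, who have no arm, and by randomised patients who never start the preparation. In addition, a patient who starts the preparation and stops belongs to the safety set on either description, yet is told to leave the study. The trial compares two preparations, and AEs in such patients are among those most likely to bear on that comparison.

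**Working it through.** **Causality scales side by side**

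| Section 13.7 | AE form |
|---|---|
| No relationship | Unrelated |
| (none) | Unlikely |
| Possible | Possibly |
| Probable | Related (shared) |
| Definite | Related (shared) |
| Unknown or impossible to determine | (none) |

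Two pairs match one to one. That leaves 2 of the 4 form options (Unlikely, Related) and 3 of the 5 grades in 13.7 (Probable, Definite, Unknown) without a one-to-one partner.

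**Which events are ambiguous**

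- Section 7.1 lists for the device procedure: "when using the Pure-Vu there is some risk of bowel perforation, pain, infection and bleeding".
- Section 7.2 lists for the preparation: "nausea with or without vomiting, abdominal pain and dehydration".
- The overlap between the two lists is pain.
- Events that start before the procedure day can be separated by date. For the procedure day itself the form records onset as a date without a time. Appendix A runs preparation over days -1 to 0, while the synopsis puts the split dose under the day before. The preparation flow charts in Appendices B1 and B2 are not in the text available, so how far the two exposures share the procedure day cannot be settled here.

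**Effect of one misassigned event**

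Inputs: up to 100 patients (section 9.0), hence 100/2 = 50 per arm if all are randomised; or 15 per arm at each site (section 9.0) times 3 sites (synopsis) = 45 per arm, 90 in all. Section 9.0 itself gives up to 10 sites; the limit of 100 patients still applies.

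- Overall: 1/100 = 1.0 point; 1/90 = 1.1 points.
- In one arm: 1/50 = 2.0 points; 1/45 = 2.2 points.

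**Effect of the safety set**

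The protocol gives no screen-failure or AE rate, so these are assumptions. Take 100 consented patients, 5 of them with an AE, and 0 to 20 who never take the preparation. The rate is 5/100 = 5.0% under 12.4, and 5/100 = 5.0% to 5/80 = 6.3% under 12.5. Within an arm of 50 randomised, with 5 AE patients and 2 to 5 who never start, it is 5/50 = 10.0% against 5/48 = 10.4% to 5/45 = 11.1%.

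**Related passages that differ**

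- Follow-up call: 2 to 3 working days (synopsis), 48 hours plus or minus 48 hours (section 9.0), 2 working days (Post-Examination Follow-up). After a Thursday procedure the third working day is Tuesday, 5 x 24 = 120 hours later, outside the 96-hour upper limit.
- Reporting: section 13.11 gives 24 hours with an outer limit of 10 working days; the AE form gives 48 hours for SAEs.
- AE outcome: four categories in section 13.8 and five different ones on the form.

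**The case against.** The strongest reply is that the protocol provides for device causality outside this one item. The synopsis names Pure-Vu as the study product, which is the object of section 13.7. Section 13.10 requires the investigator to decide whether an event is device related, because that decision governs how long it is followed, and it collects AEs in source documents as well as on the form. The form also has a description field. Its presets of tissue trauma, excessive bleeding and laceration are not on the preparation's list of main risks, and nausea, vomiting and dehydration are not on the procedure's list.

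Most of this stands, and it rules out three stronger readings that a reader might infer.

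- *That the device-related rate is lost, or that no event from the procedure day onward can be attributed.* The documents do not support this. Descriptions separate many events, and the investigator's judgement exists. But a description is not a causality assessment, and using source documents means reconstruction outside the form. Device-effect reports under section 13.11 may be only a partial route, since the word unanticipated there can be read as qualifying the whole list.
- *That patients who do not complete the preparation are, by rule, not followed for AEs.* Section 11.1.3 limits follow-up to those who receive study-assigned procedures, but section 11.1.2 calls the preparation itself a procedure, and sections 12.5 and 13.1 point to inclusion. Withdrawal reasons, the diary and the tolerability questions could also bring intolerance to light. What remains is a conflict with section 11.1.5.
- *That one misassigned event, at about three times the 0.35% risk quoted in section 7.1, measures the harm.* Any single event among 90 to 100 patients gives that ratio, with or without a causality problem, and the 0.35% concerns colonoscopy risks rather than all mild AEs.

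It is also fair that section 12.5 may be a minimum inclusion rule rather than a full definition, and that this is an unpowered pilot in which AEs are summarised without a test.

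**Conclusion.** The point holds in a limited form. The form's causality item is not directed at the device and does not carry the protocol's own scale. For events that either exposure could cause, a named secondary endpoint therefore depends on recovery from outside the form. One such event is worth about 1 point overall or 2 points in an arm, assuming 90 to 100 patients split evenly. How often it would occur, and whether it would favour one arm, cannot be stated from the protocol. The overall AE rate and the primary endpoint are unaffected by the causality item.

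The safety-set conflict is real but milder: up to about 1.3 points overall under the assumed figures (6.3% against 5.0%). The wording on patients who do not complete the preparation creates a risk of under-recording of unknown size. The differences in call timing, reporting limits and outcome lists are secondary. The whole is worth correcting before the form is used, because attribution is much harder to recover afterwards.

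**What to change.** 1. Relabel the form item as relationship to Pure-Vu, with the five grades of section 13.7, and have section 13.7 name the device in place of study treatment. A separate item for the preparation is optional, as no endpoint requires it.
2. State one safety set in sections 12.4 and 12.5 for the overall AE rate: all randomised patients who took any of the assigned preparation, by arm.
3. Report the device-related rate among patients in whom Pure-Vu was used. Using the set in item 2 would put patients never exposed to the device into the denominator and dilute the rate.
4. Clarify in sections 11.1.3 and 11.1.5 that not having the procedure does not end AE collection for patients in the safety set, and say when their follow-up contact is timed.
5. Reconcile the passages on call timing, SAE reporting limits and AE outcome categories.

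The cost is protocol wording, a small revision of the case report form before first use, and a few extra calls to patients who did not have the procedure.
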